#### **9.4.1.2. Analyses of Secondary Efficacy Endpoints**

##### **9.4.1.2.1. Analyses of Key Secondary Endpoints**

Key secondary endpoints (defined in [Table 4](#)) and corresponding estimands (defined in Section [10.2](#)) will be analyzed as follows:

For time to Complete TMA Response (Section [3.2.1](#)), participants will be assigned as responders at the time of their response and will be censored at the earliest of their discontinuation time or at the end of available follow-up if they have not responded by then. The corresponding estimand is the hazard ratio of time to Complete TMA Response between treatment groups in participants in the mITT. A hypothetical strategy will be applied where all data after intercurrent events of premature discontinuation of study treatment or initiation of disallowed therapy or medicine will be censored. Kaplan-Meier cumulative distribution curves will be generated for each treatment group, and a log-rank test comparing the curves will be performed. A corresponding summary table will present by treatment group the cumulative distribution function estimate, the number of participants at risk, the number of participants responding, and the number of participants censored at each post-baseline time point. The table will also present the first quartile, median, and third quartile, along with the corresponding 2-sided 95% CI, of time to response.

For hematologic response at Week 26 and on dialysis at Week 26, the corresponding estimand is the difference in the proportion of participants achieving hematologic response at Week 26 or difference in the proportion of participants on dialysis at Week 26 respectively, between treatment groups in participants in the mITT. Analyses will be based on a composite strategy where participants will be considered as nonresponders after intercurrent events of premature discontinuation of treatment or initiation of disallowed therapy or medicine. Following a similar approach as for the analyses of the primary estimand, a Cochran-Mantel-Haenszel test will be applied and NRI method will be used to handle missing data.

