3. LIST OF ABBREVIATIONS AND DEFINITIONS OF TERMS

The following abbreviations and acronyms are used in this statistical analysis plan (SAP).

Abbreviation or acronym	Explanation		
ADA	antidrug antibody		
ADAMTS13	a disintegrin and metalloproteinase with a thrombospondin type 1 motif,		
	member 13		
AE	adverse event		
AESI	adverse event of special interest		
aHUS	atypical hemolytic uremic syndrome		
BSC	best supportive care		
C5	complement component 5		
CI	confidence interval		
CIF	cumulative incidence function		
CKD	chronic kidney disease		
CKD-Epi	CKD-Epidemiology Collaboration		
COVID-19	coronavirus disease 2019		
EC	exclusion criteria		
ECG	electrocardiogram		
eGFR	estimated glomerular filtration rate		
EQ-5D-5L	EuroQol 5-Dimension 5-Level		
FACIT-Fatigue	Functional Assessment of Chronic Illness Therapy-Fatigue		
IC	inclusion criteria		
ITT	intent-to-treat		
IV	intravenous(ly)		
KDQOL-36	Kidney Disease Quality of Life instrument [™] –36 items		
LDH	lactate dehydrogenase		
MACE	major adverse cardiovascular event		
MedDRA	Medical Dictionary for Regulatory Activities		
mITT	modified intent-to-treat		
NRI	nonresponder imputation		
PA2	Protocol Amendment 2		
PD	pharmacodynamic(s)		
РК	pharmacokinetic(s)		
PPS	Per-Protocol Set		
q8w	every 8 weeks		
QTc	corrected QT		
QTcF	QT interval corrected for heart rate using Fridericia's formula		
RBC	red blood cell		
SAE	serious adverse event		
SAS®	Statistical Analysis Software®		
SAP	statistical analysis plan		
SD	standard deviation		
SF-12	Short-Form Health Survey 12 Item		
SoA	schedule of activities		
SOC	System Organ Class		
SOP	standard operating procedure		
SSc-TMA	systemic sclerosis-associated thrombotic microangiopathy		
ST-HUS	Shiga toxin-related hemolytic uremic syndrome		
TEAE	treatment-emergent adverse event		

Table 1:Abbreviations and Acronyms

Abbreviation or acronym	Explanation	
TESAE	treatment-emergent serious adverse event	
ТМА	thrombotic microangiopathy	
ТТР	thrombotic thrombocytopenic purpura	
ТТО	time trade-off	
VAS	visual analogue scale	
WHO	World Health Organization	

4. **DESCRIPTION OF THE PROTOCOL**

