4.2. Changes from Analyses Specified in the Protocol

As mentioned in Section 4.1, the planned interim analysis for sample size re-estimation and the planned primary analysis as specified in Protocol Amendment 2 (PA2) will not be conducted due to the termination of the study. Only the final study analysis after the last participant in the study has completed the 26-week Treatment Period will be performed.

In addition, no hypothesis testing or inferential statistics for the purpose of treatment comparisons will be performed due to the reduction in sample size because of few participants enrolled. Estimands defined in PA2 are no longer applicable and, thus, are removed from the SAP.

SAP Version	Version Date	Change	Rationale
1.0	29 Jun 2021	Not applicable	Original version
2.0	DD MMM 2022	 Changes to align with PA2: Added additional secondary endpoints: Loss of TMA response Changes from Baseline in hematologic parameters at all scheduled visits Increases in hemoglobin ≥ 1 g/dL at Week 26 Elevated "change in patient-reported outcomes as measured by FACIT-Fatigue" to the secondary endpoint Added an exploratory endpoint to assess overall survival Added the Modified Intent-to-Treat Set as the primary analysis set; removed the Enrolled Set Updated the Per-Protocol Set definition to reflect the revised inclusion/exclusion criteria Changes from analyses specified in PA2: Removed the interim analysis for sample size re-estimation and the primary analysis Removed descriptions on estimands corresponding to the primary and key secondary endpoints Combined key secondary endpoints and additional secondary endpoints will be summarized in descriptive statistics 	To reflect changes made in PA2 and in the planned analyses due to the early termination of the study

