5.3. Exploratory Endpoints

The exploratory endpoints of the study are as follows:

- Exploratory biomarkers will be assessed in blood and urine for change from Baseline and may include, but are not limited to, markers of vascular damage, renal injury, and complement dysregulation (eg, soluble terminal complement complex, factor Ba). Exploratory biomarker assessments will be detailed in a separate, exploratory biomarker SAP.
- Change in patient-reported outcomes as measured by EuroQol 5-Dimension 5-Level (EQ-5D-5L) and Kidney Disease Quality of Life instrument[™]-36 items (KDQOL-36) at scheduled visits
- 3. Incidence of complement dysregulation-related mutations
- 4. Health resource utilization by Week 26 and Week 52 including:
 - Number, underlying reason, and duration of hospitalizations (including stays in intensive care unit, if applicable)
 - Number of outpatient medical encounters (including physician or emergency room visits)
- 5. Overall survival by Week 26 and Week 52

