7.1.1. Handling Missing Data

For binary endpoints, a nonresponder imputation (NRI) method will be used by categorizing any participants who have a missing value for categorical variables at a specific visit as a nonresponder for that visit. In addition, participants who have the following intercurrent events will be assigned as nonresponders, regardless of whether any response is observed after these intercurrent events: premature discontinuation of the study treatment or initiation of disallowed therapy or medicine, before observing the response for an endpoint in analysis.

For time-to-event endpoints (time to complete TMA response, time to response for each individual TMA parameter), missing data and data after intercurrent events of premature discontinuation of study treatment or initiation of disallowed therapy or medicine will be censored.

For the continuous secondary endpoint, no missing data handling will be performed. Summary statistics will be provided using observed data.

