7.3.1. Primary Analysis

The primary efficacy endpoint of the study is complete TMA response during the 26-week randomized Treatment Period.

Analysis of the primary endpoint will be conducted on the mITT Set based on randomized treatment groups using NRI for missing data handling. Point estimate and 95% confidence interval (CI) will be provided for the response rate for each treatment group. For participants who withdraw from the study, data up to the time of withdrawal will be used to assess complete TMA response.

Additionally, the primary efficacy endpoint will be analyzed based on the PPS.

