7.3.2. Secondary Analyses

All secondary analyses will be performed on the mITT Set.

For time-to-event endpoints, Kaplan-Meier cumulative distribution curves will be generated for each treatment group. A corresponding summary table will present by treatment group the cumulative distribution function estimate, the number of participants at risk, the number of participants responding, and the number of participants censored at each post-Baseline time point. The table will also present the first quartile, median, and third quartile, along with the corresponding 2-sided 95% CI, of time to response.

The binary additional secondary endpoints will be summarized by randomized treatment group by calculating the point estimate and 2-sided 95% CI for the response rate, based on exact confidence limits using the Clopper-Pearson method (Clopper, 1934). NRI will be used to handle missing data.

For continuous additional secondary endpoints, descriptive statistics, including the number of participants, mean, SD, minimum, median, and maximum, will be provided based on observed data.

For participants who require dialysis, change from Baseline in dialysis requirements will be summarized. An analysis will present the number and proportion of participants who require dialysis over time. A 2-sided 95% CI for the proportion will be provided. A participant will be considered as not requiring dialysis at a specific post-Baseline time point if they have been dialysis free for at least 14 days prior to that time point.

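### Kaplan-Meier curves for time to response censor at discontinuation, disallowed therapy and, by implication, death, so they can sit above the nonresponder-imputed rate for the same endpoint

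*SAP*

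**What the plan says.** The SAP handles Complete TMA Response in two ways.

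- **As a binary endpoint.** SAP 7.3.1: "Analysis of the primary endpoint will be conducted on the mITT Set based on randomized treatment groups using NRI for missing data handling". Under SAP 5.1 and 7.1.1, a participant who stops study treatment early or starts a disallowed therapy before responding is a nonresponder and stays in the denominator.
- **As a time-to-event endpoint.** SAP 7.1.1 censors missing data, and adds that "data after intercurrent events of premature discontinuation of study treatment or initiation of disallowed therapy or medicine will be censored". The rule also covers time to response for each TMA parameter. SAP 7.3.2: "For time-to-event endpoints, Kaplan-Meier cumulative distribution curves will be generated for each treatment group", with a table of the estimated distribution, the numbers at risk, responding and censored, and the quartiles.

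The protocol (9.4.1.2.1) has the same censoring. Participants "will be censored at the earliest of their discontinuation time or at the end of available follow-up if they have not responded by then". It names the approach: "A hypothetical strategy will be applied where all data after intercurrent events" of these two kinds are censored. Its binary rule is a composite strategy (9.4.1.1). After early termination, SAP 4.2 states: "Estimands defined in PA2 are no longer applicable and, thus, are removed from the SAP". Both handling rules remain in the SAP without those labels.

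Neither document names death in the censoring rule. It can enter only as missing data (SAP) or as the end of available follow-up (protocol). Yet SAP 5.3 lists as an exploratory endpoint "Overall survival by Week 26 and Week 52".

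**The concern.** Kaplan-Meier treats a censored participant as someone who would have gone on to respond at the same rate as those still followed. That is hard to accept here. Protocol 2.2 describes plasma exchange or infusion as part of typical treatment, and Protocol 6.6.2 disallows it after randomization during the Treatment Period; starting it plausibly signals TMA that is not resolving. Severe uncontrolled infection is among the mandatory reasons for stopping study drug (Protocol 7.1). After death there is no later response to estimate.

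The analysis is now descriptive only, so the curves and quartiles are themselves the result. Protocol 4.2.2 says time to response is meant to guide prescribers. A reader could see one response figure in the primary table and a higher one at Week 26 on the curve, and the SAP does not say that the two answer different questions. The excess can also differ between arms and so alter the visual contrast.

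**Working it through.** The documents give no figure comparing the two estimates. Their one related figure, about 90% power (Protocol 9.2, SAP 9.2), agrees with exact enumeration: Fisher's test has 88.3% power with 45 per arm (50 less 10% dropout) at 35% against 70%. It has no bearing on this point beyond supplying the rates used below.

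**Inputs.** 16 enrolled and 1:1 allocation (SAP 4); 8 per arm is an assumption from these. Response rates of 35% and 70% and dropout of 10% come from SAP 9.2. The share of an arm with discontinuation, disallowed therapy or death before response is not stated anywhere, so it is varied from 5% to 30%.

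**Direction.** Kaplan-Meier passes the weight of each censored participant to those still at risk. One minus Kaplan-Meier at Week 26 therefore cannot fall below responders/N. It exceeds it when someone is censored before a later response in that arm; otherwise the two are equal. With two responders among eight and nobody censored early, both give 2/8 = 25%.

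**Small example.** If c of 8 are censored before the first response, the rest are followed to Week 26 and r respond, then Kaplan-Meier gives r/(8 − c) and nonresponder imputation gives r/8. With c = 1 and r = 4: 4/7 = 57% against 4/8 = 50%.

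**Example with spread timing.** Eight in an arm, responses at Weeks 2, 4 and 8, intercurrent events or deaths at Weeks 1 and 3, three others followed to Week 26. The numbers at risk at the three responses are 7, 5 and 4.

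- Kaplan-Meier: 1 − (6/7 × 4/5 × 3/4) = 48.6%.
- Nonresponder imputation: 3/8 = 37.5%.
- Cumulative incidence with the two events as competing: 1/8 + 1/8 + 1/8 = 37.5%.
- The two kept at risk to Week 26 as nonresponders: also 37.5%.

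**Large-sample gap.** With constant hazards over 26 weeks, let a = −ln(1 − R), where R is the Kaplan-Meier rate, and let m be the cumulative hazard of the events. Then the share with an event before response is m/(a + m) × (1 − e^−(a+m)), and the nonresponder-imputed rate is a/(a + m) × (1 − e^−(a+m)). For R = 0.70 and a share of 10%: a = 1.204, m = 0.185, rate = 65.1%.

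| Assumed share | Rate when Kaplan-Meier is 70% (gap, points) | Rate when Kaplan-Meier is 35% (gap, points) |
|---|---|---|
| 5% | 67.6% (2.4) | 34.0% (1.0) |
| 10% | 65.1% (4.9) | 33.0% (2.0) |
| 20% | 59.9% (10.1) | 30.8% (4.2) |
| 30% | 54.5% (15.5) | 28.6% (6.4) |

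Simulation with 8 per arm, the protocol's visit weeks and a 10% share gave mean gaps of 5.4 points at 70% and 2.3 at 35%. In no run was Kaplan-Meier the lower of the two.

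**Quartiles.** With one loss among eight before any response, the fourth response reaches the median either way (4/7 or 4/8). With two such losses and three responders, Kaplan-Meier reaches 3/6 = 50% while cumulative incidence stops at 3/8 = 37.5%, so only one of them has a median. That case is a 25% loss.

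**The case against.** The strongest reply is that this was a deliberate choice. The protocol declared a hypothetical strategy for time to response, repeated it in Table 8, and used a composite strategy for the binary endpoint. A higher Kaplan-Meier value is then what that target implies, and it is an overstatement only against the composite target. Nor is stopping study drug a true competing event: Protocol 7.1 asks such participants to continue visits, so a later response could be observed and goes uncounted by rule. Both arguments stand for a curve labelled as hypothetical. They do not cover death, and the SAP no longer carries the label.

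The consequence is also limited and partly visible. No test is planned, the table shows the numbers censored, and discontinuations and deaths are reported elsewhere (SAP 7.2.1, 7.7.2.5). The exact 95% interval for 4/8 runs from about 16% to 84%, far wider than these gaps.

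Three stronger readings are tempting but unsupported:

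- A reader might infer that the hypothetical strategy was the only justification and is now gone. SAP 4.2 drops the formal estimands because no treatment comparison will be made; the protocol text still stands.
- A reader might infer that the arm with more losses gains most. The gap also depends on response: at the same 20% share it is 10.1 points at 70% and 4.2 at 35%, and an arm with no later response gains nothing.
- A reader might take the unused abbreviation "cumulative incidence function" in SAP section 3 as proof that such an analysis was intended. It may be only an editorial leftover.

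**Conclusion.** The point holds as a matter of estimator choice and labelling. Kaplan-Meier needs censoring that is independent of response, which is implausible for death and doubtful for disallowed therapy started because TMA persists. In the SAP as it stands, the resulting curve is not described as hypothetical.

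The likely size is modest: 57% against 50% for one early loss with four responders among an assumed 8, and about 5 or 2 points at an assumed 10% share, at Kaplan-Meier rates of 70% and 35%. The 10% is borrowed from the planned dropout rate, which is not the same quantity. A reader might infer gaps as large as 60% against 37.5%, but that needs three of eight lost before any response (3/5 against 3/8), a loss rate the documents do not state. Nor is it certain that the curve and the response rate will disagree; they coincide if nobody is censored before a later response. Only descriptive output is affected.

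**What to change.** In SAP 7.1.1 and 7.3.2, report the cumulative incidence function of response by arm, with death, premature discontinuation and initiation of disallowed therapy as competing events, and derive the quartiles from it. State explicitly how death is handled. Keep the protocol's Kaplan-Meier curve as supportive and label it as hypothetical.

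Keeping these participants at risk as nonresponders to Day 183 gives the same value only if there is no other early censoring, and SAP 7.1.1 also censors missing data, so the choice should be written down.

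The cost is a sentence or two in the SAP and a standard procedure option on data already held. The downside is that medians or upper quartiles may not be reached, and the displayed response will look slightly less favourable.

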7.1.2. Multicenter Studies

The number of participants at each site is expected to be very small. Therefore, there will be no summarization of efficacy analyses by site.

7.2. Study Participants

7.2.1. Disposition of Participants

The summary of disposition will include the number and percentage of screened participants, randomized participants, and treated participants. In addition, the number and percentage of participants who discontinued from study treatment, the primary reason for treatment discontinuation (including coronavirus disease 2019 [COVID-19]-related reason) or discontinued from the study and the primary reason for study discontinuation (including COVID-19 related reason) will be summarized for all randomized participants by treatment group and overall. A table will also summarize the number and percentage of participants included in each analysis set defined in Section 6.

7.2.2. Protocol Deviations

Protocol deviations will be determined per the standard operating procedure (SOP) "Identification, Handling, and Documentation of Protocol Deviations" (SOP-G-CL-0044). The number and percentage of participants with specific protocol deviations will be summarized for all enrolled participants by important and nonimportant deviations. To ensure completeness of the list of protocol deviations, the following will be verified programmatically from the database:

- 1. Participants from whom informed consent was not obtained
- 2. Participants who violated any IC/EC
- 3. Participants who received any disallowed medication or underwent any disallowed therapeutic procedure
- 4. Participants randomized to the ravulizumab treatment group who did not receive all of the planned number of infusions during the 26-week randomized Treatment Period

Protocol deviations from monitoring reports and other relevant sources will also be reviewed, and any important deviations will be included in the list that is summarized and reported.

Summary statistics will be presented by treatment group and overall.

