**Table 7: Weight-based Doses of Ravulizumab**

Body Weight Range a	Loading Dose (Day 1)	Maintenance Doses (Days 15, 71, and 127)
≥ 30 to < 40 kg	1200 mg	2700 mg
≥ 40 to < 60 kg	2400 mg	3000 mg
≥ 60 to < 100 kg	2700 mg	3300 mg
≥ 100 kg	3000 mg	3600 mg

a Dose will be based on the last recorded study visit body weight. If the study drug is prepared the day before a visit, the weight from the most recent study visit should be used.

At the scheduled dosing visits (Section 1.3), study drug should be administered after all other tests and procedures have been completed, excluding the postdose sample collections (pharmacokinetic [PK]/pharmacodynamic [PD]/biomarkers).

During the Treatment Period, participants will be randomized 1:1 to receive blinded doses of ravulizumab or placebo:

- Participants in the ravulizumab group will receive a blinded loading dose of ravulizumab via IV infusion on Day 1, followed by a blinded maintenance dose at Day 15 then q8w thereafter through the end of the Treatment Period.
- Participants in the placebo group will receive a blinded matching placebo dose via IV infusion on Day 1, followed by a blinded matching placebo dose at Day 15, then q8w thereafter through the end of the Treatment Period.

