6.3. Per-Protocol Set

The Per-Protocol Set (PPS) will consist of mITT participants who met all of the following criteria. The primary analysis will be repeated on the PPS as supplementary analyses. PPS will be analyzed according to the participants' randomized treatment assignment.

- 1. Participants who received full randomized intervention during the 26-week randomized Treatment Period
- 2. Did not receive any disallowed medications or undergo any disallowed therapeutic procedures as described in Protocol Section 6.6.2:
 - Experimental interventions or therapies
 - Eculizumab or other agents that act on the complement pathway
 - Therapeutic plasma exchange/plasma infusion following randomization
- 3. Met inclusion criteria (IC) in the study:
 - IC 4: TMA within ≤ 14 days prior to Screening is associated with at least one of the following triggers:
 - a) Autoimmune (lupus nephritis or systemic sclerosis-associated TMA [SSc-TMA])
 - b) Infection
 - c) Solid organ transplant (eg, kidney, pancreas, liver, heart, or small bowel)
 - d) Drugs
 - e) Malignant hypertension

- IC 5: Confirmation of all of the following laboratory findings during the Screening Period and/or ≤ 14 days prior to the start of the Screening Period:
 - a) Platelet count $< 150,000/\mu$ L
 - b) $LDH \ge 1.5 \times upper limit of normal and hemoglobin \le LLN (based on age and sex)$
 - c) Acute kidney injury as defined by meeting 1 or more of the following criteria (for kidney transplant recipients, the pre-TMA value is based on post-transplant eGFR):
 - Acute decline in eGFR \geq 50% from pre-TMA value (the pre-TMA value must be \leq 12 months prior to Screening)
 - New acute kidney injury with an eGFR \leq 30 mL/min/1.73 m²
 - New initiation of dialysis due to TMA requiring > 1 session and for no more than 14 days prior to Screening
- 4. Did not violate important exclusion criteria (EC) in the study, including the following:
 - EC 1: Any known gene mutation that causes aHUS
 - EC 3: Known chronic kidney disease (CKD):
 - In participants with native kidneys: $eGFR \le 45 \text{ mL/min}/1.73 \text{ m}^2$ by the CKD-Epidemiology Collaboration (CKD-Epi) equation (Levey, 2009) due to any cause or ongoing acute kidney injury requiring dialysis treatment lasting for > 14 days prior to Screening.
 - In kidney transplant recipients: determination of the CKD threshold will be based on Investigator judgment.
 - EC 5: Primary and secondary glomerular diseases other than lupus

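### The programmatic check for missed infusions covers only the ravulizumab group, so deviation counts by treatment group are open to unequal ascertainment

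*SAP*

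**What the plan says.** SAP 7.2.2 (Protocol Deviations) has deviations determined under a sponsor SOP and summarised for all enrolled participants as important or nonimportant. It then adds a back-up: "To ensure completeness of the list of protocol deviations, the following will be verified programmatically from the database". Four checks follow. The first three (consent, eligibility criteria, disallowed medication or procedure) carry no limit by group. The fourth, which looks at the 26-week Treatment Period, does: "Participants randomized to the ravulizumab treatment group who did not receive all of the planned number of infusions". No reason is given for the restriction.

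The section then adds a third source: "Protocol deviations from monitoring reports and other relevant sources will also be reviewed, and any important deviations will be included in the list". It ends by stating how the results are shown: "Summary statistics will be presented by treatment group and overall".

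Elsewhere the two groups are treated alike. Protocol 6.1 gives placebo on the ravulizumab timetable ("Participants in the placebo group will receive a blinded matching placebo dose via IV infusion on Day 1", then Day 15 and every 8 weeks). Protocol 6.4 has the date and time of each dose entered on the CRF. The first Per-Protocol criterion in SAP 6.3 is worded for both groups: "Participants who received full randomized intervention during the 26-week randomized Treatment Period".

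**The concern.** A deviation table split by treatment group is read as a comparison of trial conduct between groups. That reading needs deviations to be sought equally hard in each. Here one type, an incomplete infusion course, has a systematic database search in the ravulizumab group and none in the placebo group. Any difference in the recorded count could then reflect the search and not the conduct.

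The other sources do not clearly close the gap. The table includes nonimportant deviations, but from monitoring and other sources only important ones are expressly added. A missed placebo infusion judged nonimportant therefore depends on the SOP, which is not among the documents. The deviation table could also disagree with the SAP's own compliance output, which would show missed placebo infusions that the deviation table omits.

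**Working it through.** The plan states no figure on this point, so the check is mainly a comparison of sections.

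**1. Is there a design reason for a one-group check?** Planned infusions per participant: 1 loading dose (Day 1) + 3 maintenance doses (Days 15, 71 and 127) = 4 (Protocol 6.1, Table 7). Placebo follows the same days. Early termination does not remove the need, because SAP 4 has the study end once the last participant in treatment completes the 26-week Treatment Period. The dosing data exist for both groups (Protocol 6.4). Nothing in the design explains the restriction.

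**2. By what stated routes can a missed infusion enter the deviation list?** (SAP 7.2.2)

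| Missed infusion | SOP | Database check 4 | Monitoring and other sources |
|---|---|---|---|
| Ravulizumab, important | yes | yes | yes |
| Ravulizumab, nonimportant | yes | yes | not expressly added |
| Placebo, important | yes | no | yes |
| Placebo, nonimportant | yes | no | not expressly added |

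The groups differ only in the database check. If the other routes work alike in both, that check can add entries for ravulizumab and never for placebo, so the direction of any distortion is fixed.

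**3. How large could it be?** The documents do not say how completely the other routes capture missed infusions, so this is an illustration with assumed values. Let n be participants per group, m the true probability of missing at least one infusion (equal in both groups), and s the share of placebo cases caught by the other routes. Capture in ravulizumab is taken as complete.

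Expected gap (ravulizumab minus placebo) = n × m × (1 − s)

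SAP 4 gives 16 enrolled but no count by group. An even split, n = 8, is assumed.

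| m | s = 0 | s = 0.5 | s = 0.8 | s = 1 |
|---|---|---|---|---|
| 10% | 0.8 | 0.4 | 0.16 | 0 |
| 20% | 1.6 | 0.8 | 0.32 | 0 |
| 30% | 2.4 | 1.2 | 0.48 | 0 |

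For example, 8 × 0.20 × (1 − 0.5) = 0.8 participants. With 8 per group, one participant is 1/8 = 12.5% of a group in that table.

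**4. What else could depend on check 4?**
- Primary summary (SAP 7.3.1): mITT Set, which SAP 6.2 defines without reference to deviations. Not affected.
- Compliance (SAP 7.7.1): infusions received over infusions expected, for the whole Safety Set, which includes placebo recipients. Not affected.
- Per-Protocol Set (SAP 6.3): the adherence criterion applies to both groups, and the section does not say that membership is taken from the deviation list. Not affected as worded.
- Missing doses (SAP 7.7.3.6): summarised by treatment group in the mITT Set. This sits under the COVID-19 heading and may be narrower in scope, so it is weaker reassurance than the compliance summary.

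**The case against.** The strongest reply is that check 4 is only a back-up. The list is first built under an SOP with no stated limit by group, and the monitoring review has none either. If those routes work well, no placebo case is lost and the gap is zero. This stands: unequal ascertainment is a risk and not an established bias. It does not justify the restriction, because a completeness check exists for cases where the other routes fail.

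It is also fair to say that little hangs on the table. The trial stopped with 16 enrolled, and SAP 4.2 rules out hypothesis testing and inferential treatment comparisons.

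Several stronger readings are tempting, and the documents do not support them:
- *Placebo non-adherence goes unverified.* It does not. Doses are on the CRF and compliance is summarised for the whole Safety Set. What lacks a database check is entry of the missed infusion on the deviation list.
- *Placebo participants with missed infusions would wrongly stay in the Per-Protocol Set.* That would require the set to be built from the deviation list, which no section states. Applied as written, SAP 6.3 excludes them.
- *Half the participants are unchecked.* Only one of the four checks is restricted; the other three cover everyone.
- *The check forces early use of treatment codes.* The documents do not say when the deviation list is finalised, and the planned summary by group needs the codes in any case.

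**Conclusion.** The point holds as a minor drafting inconsistency. One of four completeness checks is limited to the ravulizumab group without a stated reason, while the results are presented by group. The count of participants with missed infusions is therefore open to unequal ascertainment that can only raise ravulizumab relative to placebo. The direction rests on the SOP and monitoring working alike in both groups.

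The size cannot be determined from the documents. The illustrative range, from no gap to 2.4 participants, depends on the assumed even split, the assumed 10% to 30% rate and the unknown capture by other routes. The effect is confined to the deviation table of a descriptive analysis. No response-rate estimate is shown to change.

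**What to change.** In SAP 7.2.2, remove the group restriction from item 4. The check should then identify any participant who missed one or more planned infusions of study drug, whether ravulizumab or placebo, in the 26-week randomized Treatment Period. If the restriction is deliberate, state the reason there and footnote the deviation table to say that this check was run in one group only.

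The cost is one phrase in the SAP and one filter removed from a program. No new data are needed, and the revised check can be run without treatment codes.
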